5.5.2 Secondary Endpoints

The secondary efficacy endpoint is the proportion of subjects with clinical success defined as a score of clear or almost clear (score of 0 or 1) on the Investigator Global Assessment (IGA) at Visit 4/Week 12 (Day 84).

Equivalent Efficacy

The compound hypothesis to be tested for clinical equivalence between test and reference is:

$$H_0: p_T - p_R < -0.20 \text{ or } p_T - p_R > 0.20 \text{ versus}$$

$$H_A: -0.20 \leq p_T - p_R \leq 0.20.$$

Where p_T and p_R are the proportions of subjects with clinical success at Visit 4/Week 12 (Day 84) for the test and reference products, respectively. The test product will be considered to be therapeutically equivalent to the reference product if the 90% CI on the difference in their proportions of subjects with clinical success, calculated by Wald's method with Yates' continuity correction, is contained within the limits -0.20 to +0.20. Rejection of the null hypothesis supports the conclusion of therapeutic equivalence between the test and reference products for the secondary efficacy variable.

The result of the analysis in the PP population will be considered definitive and that in the mITT population as supportive.

Analysis for therapeutic equivalence will be performed based on the following SAS code (SAS Institute v.9.1.3):

P-value is chosen from Continuity Adj. Chi-Square test.

The SAS code for 90% confidence interval (trt=1 for Test, trt=2 for Reference):

```
proc freq data=XX ;  
  where trt in (1,2);  
  tables trt* success / alpha=0.10 riskdiff;  
  output out=CIDIFF (keep= l_rdif2 u_rdif2 ) riskdiff;  
run;
```

For the final 90% continuity-corrected CI, the lower limit = (l_rdif2 - yates) and the upper limit = (u_rdif2 + yates), where yates, the Yates' continuity-correction factor, is derived as $(1/n1+1/n2)/2$, n1=number of subjects in Test arm and n2=number of subjects in Reference arm.

Superiority

The hypotheses to be tested for superiority of the test and reference products over Vehicle are:

$$H_0: p_T \leq p_V \text{ versus } H_A: p_T > p_V$$

$$H_0: p_R \leq p_V \text{ versus } H_A: p_R > p_V$$

Where p_T , p_R and p_V are the proportions of subjects with clinical success at Visit 4/Week 12 (Day 84) for the test, reference and Vehicle products, respectively. The tests will be conducted independently for the test product vs. vehicle and the reference product vs. vehicle using two-sided, $\alpha = 0.05$, continuity-corrected Z-tests. Superiority will be established if the

proportion of subjects with clinical success in the active treatment group is greater than and statistically different ($p < 0.05$) from that in the Vehicle. Rejection of the null hypothesis supports the conclusion of superiority of the test and reference products over the Vehicle product for the secondary efficacy variable.

The analyses in the mITT population will be considered primary and those in the PP population as supportive.

Analysis for superiority will be performed based on the following SAS code (SAS Institute v.9.1.3):

The SAS code for p-value (trt=2 for Reference vs. trt=3 for Vehicle):

```
proc freq data=XX ;  
  where trt in (2,3);  
  table trt * success /chisq ;  
run;
```

5.5.3

[REDACTED]

[REDACTED]

5.6 Safety Variables and Analyses

Duration of Treatment and Medication Compliance

Number of applications, days of exposure, and compliance rate will be summarized by treatment group using descriptive statistics. For each subject, the overall duration of treatment (days) will be calculated using the following formula:

$$(\text{Date of last application of study medication}) - (\text{Date of first application of study medication}) + 1.$$

Medication compliance rate (%) will be calculated for each subject as follows:

$$(\text{Total number of applications used}) / (\text{Expected number of applications}) * 100\%.$$

[REDACTED]

Adverse Events

Adverse events (AEs) will be coded in MedDRA, version 18.1. Treatment-Emergent Adverse Event (TEAE) is defined as any AE occurs on or after application of the first dose of study drug. Number and percent of subjects reporting TEAEs will be tabulated by treatment group. Summaries will be presented by body system and preferred term for the ITT population, and

further by severity and relationship to study medication. TEAEs reported by 5% or more subjects for any treatment group will also be summarized. In the summaries of incidence rates (frequencies and percentages), severity and relationship to study drug, subjects who report more than one event that are mapped to the same preferred term will be counted only once under the strongest severity and relationship, accordingly. The difference between Test and Reference treatments with regard to the severity and frequency of their dermatological adverse events will be statistically evaluated. Chi-Square or Fisher's exact test will be used to compare the proportions of subjects of the two active treatment groups who report any TEAE.

Treatment-Emergent Serious Adverse Events (TESAEs) will be discussed within the clinical study report. TEAEs, TESAEs and TEAEs that led to treatment interruption or discontinuation will be presented in data listings.

Concomitant Medications, Laboratory Values, and Vitals Signs

Concomitant medications will be coded using the WHO Drug Dictionary, version September 2015, and will be presented in data listings. All vital signs data will be displayed in listings.

Erythema Severity and Application Site Reaction Assessments

Frequency and distribution of erythema severity assessment and application site reactions of dryness, scaling/peeling, pruritus, burning/stinging, pain and will be summarized and compared descriptively by visit.

Safety comparisons will be performed only for the ITT population.

6 Appendices

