7.2 Definitions

An adverse event (AE) is defined as any untoward medical occurrence in a subject administered a medicinal product and which does not necessarily have to have a causal relationship with this treatment. An adverse event canister therefore be any unfavorable and unintended sign (for example, an abnormal laboratory finding), symptom, or disease temporally associated with the use of a medicinal product, whether or not considered related to this medicinal product.

A serious adverse event (SAE) is an adverse event that results in any of the following outcomes:

- Death
- Life-threatening event (i.e., the subject was, in the opinion of the investigator, at immediate risk of death from the event as it occurred. It does not include an event that, had it occurred in a more severe form, might have caused death.)
- Requires in-subject hospitalization or prolongs hospitalization
- A persistent or significant disability/incapacity or substantial disruption of the ability to conduct normal life functions
- Congenital anomaly/birth defect
- Other adverse events that may be considered serious based upon appropriate medical judgment, may jeopardize the subject and may require medical or surgical intervention to prevent one of the outcomes listed above.

Immediately Reportable Adverse Events (IRAE): Any serious AE or any AE that necessitates discontinuation of study medication, including pregnancy.

Unexpected Adverse Event: An unexpected event is any adverse drug experience, the specificity or severity of which is not consistent with the current approved product labeling (package insert) for the study medication, the Investigator's Brochure, or as described in the clinical protocol and consent materials.

Intensity of Adverse Events: The maximum intensity of an AE during a day should be recorded on the CRF. If the intensity of an AE changes over a number of days, then separate entries should be made having distinct onset dates for the changes in severity.

Protocol No: PRG-NY-16-009

Mild - AEs are usually transient, requiring no special treatment, and do not interfere with subject's daily activities.

Moderate - AEs typically introduce a low level of inconvenience or concern to the subject and may interfere with daily activities, but are usually ameliorated by simple therapeutic measures.

Severe - AEs interrupt a subject's usual daily activity and traditionally require systemic drug therapy or other treatment.

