7.3 Eliciting and Reporting of Adverse Events

The investigator will periodically assess subjects for the occurrence of adverse events.

All adverse events (as defined in Section 7.2), either observed by the Investigator or one of his/her medical collaborators, or reported by the participant spontaneously, or in response to direct questioning, will be reported and documented in the source and the study reporting forms. When reporting an adverse event, the Investigator must assign a

severity grade to each event and declare an opinion on the relatedness of the event to the study medication or procedure. Serious or unexpected adverse events must be reported to Perrigo **within 24 hours** of when the Investigator first learns of the occurrence of the event.

Adverse events will be documented in the source document and recorded in a timely manner on case report forms (CRFs). Adverse events that are identified at the last assessment visit (or the early termination visit) must be recorded on the AE CRF with the status of the AE noted.

Adverse event reporting begins from the signing of informed consent. Adverse events should be followed until resolved or 30 days after the final study treatment. In any case, serious adverse events that are not resolved or considered to be chronic within 30 days of the final study treatment must be followed by the investigator until they become resolved or are considered to be chronic (stabilized for at least 30 days). All events that are ongoing at this time will be recorded as ongoing on the CRF.

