9. CONSENT CONSIDERATIONS AND PROCEDURES

It will be made clear to the subject that, for the purposes of the study, they are consenting only for topical application of medication or vehicle. Investigators may discuss the availability of the study and the possibility for entry with a potential subject without first obtaining consent. However, informed consent must be obtained and documented prior to initiation of any procedures that are performed solely for the purpose of determining eligibility for research, including withdrawal from current medication(s). When this is done in anticipation of, or in preparation for, the research, it is considered to be part of the research.

The study must be approved in writing by an appropriate IRB as defined by FDA regulations. A copy of the Letter of Approval from the IRB, which also contains specific identification of the documents approved, must be received by Perrigo, prior to study commencement.

Periodic status reports must be submitted to the IRB at least annually as required by the site's IRB, as well as notification of completion of the study and a final report within three months of study completion or termination. A copy of all reports submitted to the IRB must be sent to Perrigo.

The investigator(s) has both ethical and legal responsibility to ensure that each subject being considered for inclusion in this study is given a full explanation of the protocol. This shall be

Protocol No: PRG-NY-16-009

documented on a written informed consent form, which shall be approved by the same Institutional Review Board (IRB) responsible for approval of this protocol. Each informed consent form shall include the elements required by FDA regulations in 21 CFR Part 50. The investigator agrees to obtain approval from Perrigo of any written informed consent form used in the study, preferably prior to submission to the IRB.

Once the appropriate essential information has been provided to the subject and fully explained by the investigators (or a qualified designee) and it is felt that the subject understands the implications of participating, the IRB-approved written informed consent form shall be signed by the subject (or their parent/legally authorized representative) and the person obtaining consent (investigator or designee). The subject shall be given a copy of the signed informed consent form and the investigator shall keep the original on file.

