6.1 Handling of Missing or Incomplete Dates for Adverse Events and Concomitant Medications

Adverse Events

Handling of partial dates is only considered for the start date. An adverse event with a partial start date is considered treatment emergent if:

- only the day is missing and the start month/year is the same or after the month/year of the first dose
- the day and month are missing and the start year is the same or greater than the year of the first dose date
- the start date is completely missing

Concomitant Medications

Handling of partial dates is only considered for the stop date. A medication with a partial stop date is considered concomitant if:

- only the day is missing and the stop month/year is the same or after the month/year of the first dose
- the day and month are missing and the stop year is the same or greater than the year of the first dose date

- the stop date is completely missing or the medication is ongoing

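### The SAP's partial-date rule counts some adverse events known to have ended before the first dose as treatment-emergent, and its timing-only TEAE definition can do the same for pre-dose events that merely improve

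*SAP*

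**What the plan says.** **Collection.** Protocol 7.3: "Adverse event reporting begins from the signing of informed consent". Events before the first application can therefore be in the database for subjects who are later dosed.

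**Recording.** Protocol 7.2 (intensity of adverse events) says that when intensity changes over several days, "separate entries should be made having distinct onset dates for the changes in severity". It does not distinguish worsening from improvement.

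**Definition.** SAP 5.6: "Treatment-Emergent Adverse Event (TEAE) is defined as any AE occurs on or after application of the first dose of study drug". It does not require the event to be new or worse than before dosing, and no visible text says how a split entry relates to the event it continues.

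**Incomplete dates.** SAP 6.1, for adverse events: "Handling of partial dates is only considered for the start date". An event is then treatment-emergent in any of three cases:
- "only the day is missing and the start month/year is the same or after the month/year of the first dose"
- with neither day nor month known, the recorded year is that of first dose or a later one
- no start date is recorded at all.

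**Use.** SAP 5.6 compares the proportion with any TEAE between Test and Reference by a chi-square or Fisher's exact test. TEAEs also feed the tables by preferred term, severity and relationship, and the summary of events reaching 5% in any group.

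**The concern.** The partial-date rule can contradict the definition it serves. An event whose recorded stop date precedes the first dose cannot have occurred on or after that dose, yet SAP 6.1 classes it as treatment-emergent when its start date is missing, or incomplete and matching. Treating an unknown start as emergent is an ordinary conservative convention. The fault is that the rule passes over a stop date that settles the question.

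The second problem arises from combining two documents. A timing-only definition is adequate when each event is one record with one onset date. It is less so when the protocol creates a fresh onset date at each change of intensity. An event that began before dosing and only got better can then acquire a post-dose record.

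What is at stake is the any-TEAE proportion, the one safety proportion for which the SAP names a test. False TEAEs raise it in every arm and pull the Test-Reference difference towards zero. In a trial meant to show that two products are comparable, that pull slightly favours the intended conclusion.

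**Working it through.** The documents give no figure to reproduce: arm sizes and the randomization ratio are blacked out, and no TEAE rate is anticipated. The check is in two parts.

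**1. Applying the rules literally.** Take an assumed first dose on 20 June and made-up records.

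| Record | SAP 5.6 / 6.1 as written | With a stop-date check |
|---|---|---|
| A. Moderate, onset 15 June, entry closed 24 June | not TEAE | not TEAE |
| A'. Same event eased to mild, new entry 25 June, ended 30 June | TEAE | TEAE |
| B. Onset June, day missing; stopped 18 June | TEAE | not TEAE |
| C. Onset same year, day and month missing; stopped 18 June | TEAE | not TEAE |
| D. Start date missing; stopped 18 June | TEAE | not TEAE |
| E. Onset May, day missing; stopped 18 June | not TEAE | not TEAE |
| F. Onset May, day missing; ongoing | not TEAE | not TEAE |

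B, C and D are misclassified: each ended two days before dosing. E and F show the limit of the problem, because a known start month before the month of first dose is handled correctly.

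A' is flagged if each entry is treated as its own AE. A stop-date check does not help there; a new-or-worsened condition is needed. Nor does the SAP's rule of counting a subject once per preferred term remove it. Entry A is not a TEAE, so the subject is counted through A'.

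**2. Size, for illustration only.** Let p be the true any-TEAE proportion in an arm. Let m be the share of subjects without a true TEAE who are flagged through a pre-dose event, assumed equal in the two arms. Then

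- observed proportion: p' = p + (1 − p)m
- observed difference: (pT − pR)(1 − m)

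All rates, m and the arm size below are assumptions.

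- 30% vs 20%, m = 3%: 0.30 + 0.70 × 0.03 = 32.1% and 0.20 + 0.80 × 0.03 = 22.4%. The difference is 9.7 points instead of 10.
- 30% vs 20%, m = 10%: 37.0% and 28.0%. The difference is 9.0 points.
- 30% vs 15%, m = 1%, 3%, 5%: the difference of 15.0 becomes 14.85, 14.55 and 14.25 points. With 200 per arm, power goes from 0.951 to 0.943, 0.923 and 0.902.
- 25% vs 20%, m = 5%: the difference goes from 5.0 to 4.75 points, and power with 200 per arm from 0.222 to 0.189.

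**The case against.** **The pre-dose window may be very short.** Protocol 5.12.1 and 5.13 list informed consent among the Visit 1/Day 1 procedures, Protocol 5.11 has the first application at the site that day, and no separate screening visit is listed. Where consent and first dose share a day, records like B to D hardly arise. This stands as a limit on size. It does not remove the problem: Protocol 9 states that "informed consent must be obtained and documented prior to initiation of any procedures that are performed solely for the purpose of determining eligibility for research", expressly including withdrawal of current medication, and refers to a screening phase. Exclusion 18 has a 30-day look-back for several drug classes, so a subject who stops such a drug in order to enter would have to consent well before Day 1. How often this happens is not visible.

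**SAP 5.6 classifies an AE, not an entry.** Protocol 7.2 describes the changing intensity of one AE, so its split entries can be read as parts of one event with one onset. A reader might infer that the plan definitely counts improving events as TEAEs. The text does not go that far; the result follows only if entries are analysed as separate AEs. That is a natural way to program from records with distinct onset dates, and nothing visible rules it out. The entry-level reading also has a merit: it captures pre-dose events that worsen after dosing, and any repair should keep that.

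**Faulty dates would be queried.** Protocol 11.1 provides for data correction forms. This reduces the number of incomplete start dates, but SAP 6.1 exists for those that remain.

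**Bias against vehicle.** A reader might infer that active products, by easing more pre-dose skin complaints, would collect more false TEAEs than vehicle. The documents do not support this. The SAP's named TEAE test is between the two active arms only. Protocol 2.2 is wider, but it compares any adverse event, and a subject with a pre-dose AE already counts there. Pre-dose dryness, stinging, itching, scaling and pain are scored on the application site scales (Protocol 5.10) and summarized by visit. Nothing shows that they would also become AE entries.

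**Conclusion.** The partial-date point holds on the text: SAP 6.1 classifies as treatment-emergent some events that fail the SAP 5.6 definition. The split-entry point holds conditionally, if entries are analysed as separate AEs.

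The effect is probably small and its size is unknown. Pre-dose events should be balanced by randomization, so the expected result is slightly higher any-TEAE proportions in all arms and a slightly diluted Test-Reference difference, by the factor (1 − m) when m is equal in both arms. Equivalence and superiority rest on the efficacy endpoints, and no safety margin or pass/fail rule uses the TEAE proportion. The reason to act is that a written rule yields a wrong classification in a tested comparison, and correcting it is cheap.

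**What to change.** **SAP 6.1.** Add that an AE with a missing or partial start date is not treatment-emergent if its stop date, or its known stop month or year, is before the first dose. Otherwise keep the present convention. Protocol 2.2 already has the AE end date recorded.

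**SAP 5.6.** Define a TEAE as an AE whose first onset is on or after the first dose, or a pre-dose AE that worsens in severity after it. Add that a post-dose entry that directly continues a pre-dose entry of the same preferred term, at equal or lower severity, is not a TEAE.

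**Cost.** A few sentences in the SAP before unblinding, some extra programming, and a review of continuing entries. The rules can be programmed from the recorded dates, terms and severity. The onset dates required by Protocol 7.2 stay as recorded, and neither the CRF nor data collection changes.

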6.1 Handling of Missing or Incomplete Dates for Adverse Events and Concomitant Medications

Adverse Events

Handling of partial dates is only considered for the start date. An adverse event with a partial start date is considered treatment emergent if:

- only the day is missing and the start month/year is the same or after the month/year of the first dose
- the day and month are missing and the start year is the same or greater than the year of the first dose date
- the start date is completely missing

Concomitant Medications

Handling of partial dates is only considered for the stop date. A medication with a partial stop date is considered concomitant if:

- only the day is missing and the stop month/year is the same or after the month/year of the first dose
- the day and month are missing and the stop year is the same or greater than the year of the first dose date

- the stop date is completely missing or the medication is ongoing

6.2 Summary of Assessments

The schedule of visits and procedures to be conducted at each visit are summarized in the Schedule of Study Procedures.
